14.3 SAFETY MONITORING

This study will utilize a Medical Monitor for safety monitoring. The medical monitor will review results throughout the clinical trial as necessary to ensure the continued safety of the device and to ensure that no subjects are exposed to unreasonable risk. The medical monitor will be available to answer all questions from investigators. The medical monitor will review and assess any reports of serious and/or device-related adverse events as well as device deficiencies that could have led to a serious adverse event, and discuss these with the reporting investigator(s) as necessary. The medical monitor, as well as any other qualified personnel designated by JJSV, shall also review any interim progress reports, as applicable.

15. PUBLICATIONS

Refer to the Clinical Trial Agreement for information regarding JJSV publication policies.

16. RISK ANALYSIS

POTENTIAL RISKS AND RISK MANAGEMENT

As part of the risk assessment and analysis, all risks were eliminated or reduced to as low as possible (or ALAP) through identified control measures. After all available control measures have been implemented; any residual risk was addressed via a Risk Benefits Analysis (RBA).

RISKS OF THE CHEETAH FEMTOSECOND LASER AND CHEETAH PI

The Cheetah femtosecond laser and Cheetah patient interface (PIs) are designed for the creation of corneal flaps for LASIK treatments. The potential risks and complications to subjects when using the Cheetah laser system in the study, include similar risks to routine use of femtosecond laser for refractive surgery with a market-approved procedure. The central wavelength [REDACTED], which is different than the IntraLase wavelength (1053nm), is commonly used in other commercial systems (VisuMax, Victus, WaveLight FS 200, Femto LDV). The Cheetah femtosecond laser and Cheetah patient interfaces are not expected to introduce new risks for flap creation.

GENERAL RISKS OF FLAP CREATION WITH A FEMTOSECOND LASER

General risks of flap creation for LASIK include a number of potential complications which may require medical treatment and/or secondary surgical intervention. These risks can include: corneal abrasion, corneal edema, corneal pain, epithelial ingrowth, epithelial defect, infection, flap de-centration, incomplete flap creation, flap tearing or incomplete lift-off, free cap, photophobia, corneal inflammation such as diffuse lamellar keratitis (DLK), corneal infiltrates and iritis, thin or thick flaps, flap striae, delayed healing, retinal

detachment, increased intraocular pressure, and hemorrhage. Complications can result in poor vision, loss of vision or loss of the eye.

RISK MANAGEMENT

Subjects will be closely monitored thought the trial duration. The occurrence of adverse events and complaints will be assessed at each study visit and reported to JJSV according to Section 11.0, Adverse Events and Product Complaints. Additionally, JJSV will monitor incoming data following the procedures outlined in Section 15.0, Monitoring. The Medical Monitor will ensure subjects are not exposed to additional risks by monitoring serious adverse events, device-related adverse events, and device-deficiencies that could have led to serious adverse events (Section 15.3, Safety Monitoring).

POTENTIAL BENEFITS

The primary benefits of laser refractive surgery with the investigational Cheetah system are the correction of myopic and hyperopic with or without astigmatic refractive errors which may reduce or eliminate the need for glasses or contact lenses for distance vision.

CONCLUSION

The hazards/risks associated with the Cheetah femtosecond laser and PIs, are acceptable and similar to those of IntraLase FS and iFS. The potential clinical benefits of the Cheetah femtosecond laser and Cheetah PIs, outweigh the residual risks when the device is used as intended.

17. RECORDS RETENTION

All study-related correspondence, subject records, consent forms, Authorization for Use/Disclosure of Health Information Forms or similar medical treatment privacy law documentation, records of the distribution and use of all study products, and original case report forms should be maintained by the investigator.

The investigator must maintain and have access to the following essential documents until notified by the Sponsor. Note: This may be for a minimum of 25 years after completion of the study unless country-specific requirements are longer. JJSV requires notification if the investigator wishes to relinquish ownership of the data so that mutually agreed-upon arrangements can be made for transfer of ownership to a suitably qualified, responsible person.

- All case report forms
- All adverse event information (detailed adverse event forms, follow-up letters, etc.)
- Investigational supply records/inventory
- IRB/IEC and regulatory approval documentation

- Study correspondence
- Study agreements
- Site visit documentation
- Protocol(s) and the reason for any deviations from the protocol
- Subject log(s)
- Clinical Investigator's Brochure
- Completed subject informed consent forms and medical privacy forms (e.g., Authorization for Use/Disclosure of Health information or equivalent documentation necessary to comply with applicable privacy laws pertaining to medical treatment in the governing countries)
- Subject medical chart/clinic notes

18. TERMINATION OF THE INVESTIGATION

The clinical investigation will be suspended in the event of high levels of complications and/or adverse events that are unexpected in nature and/or severity and evaluated as to causality relative to the study device. The clinical investigation may be suspended if the Medical Monitor or IRB/IEC, upon review and evaluation of the clinical data, finds unacceptable clinical performance or the level of single or total complications and/or adverse events unacceptable for continuation of the investigation.

If causality is shown not to be related to the study device, the study may be resumed in accordance with the IRB/IEC and regulations of the FDA and governing countries. The study will be terminated if causality is shown to be related to the study device.

Additionally, the investigator, or JJSV, may stop a subject's participation at any time. JJSV may also stop the study at any time for reasons it determines appropriate. However, no suspension of the study would be made to disadvantage the study subjects. Following suspension of the study for any reason, all study subjects who have already received treatment would continue to be followed through completion of the study visit schedule.

19. STATISTICAL METHODS

This section highlights the analyses for the primary study endpoints as well as other study endpoints. [REDACTED]

[REDACTED]

19.1 ANALYSIS POPULATION

[REDACTED]

[REDACTED]

[REDACTED]

The analysis population [REDACTED] will be both eyes of [REDACTED] treated subjects and will be used for all endpoints. [REDACTED]
[REDACTED]
[REDACTED]
[REDACTED]
[REDACTED]
[REDACTED]
[REDACTED]
[REDACTED]
[REDACTED]

19.2 PRIMARY STUDY ENDPOINTS

[REDACTED] surface quality, [REDACTED] of the study eye will be evaluated relative to the control eye on a scale of 1 to 5 [REDACTED]. A score of 3 means that the study eye is similar to the control eye; a score of 4 means that the study eye is superior to the control eye; a score of 5 means that the study eye is much better than the control eye; a score of 1 means that the control eye is much better than the study eye and a score of 2 means the control eye is superior to the study eye.

[REDACTED]
[REDACTED]

At least 90% of subjects are expected to have a score equal to or greater than 3 for [REDACTED]
[REDACTED]

[figure not shown]
19.3 ADDITIONAL ENDPOINTS

[REDACTED]
[REDACTED]
[REDACTED]
[REDACTED]
[REDACTED]
[REDACTED]
[REDACTED]
[REDACTED]
[REDACTED]
[REDACTED]

[REDACTED] Summary statistics (mean, standard deviation, minimum and maximum) will be reported for [REDACTED]
[REDACTED] flap thickness (from OCT) [REDACTED].

[REDACTED]
[REDACTED]

The incidence of adverse events will be summarized by AE type.

19.4  GENERAL STATISTICS

Descriptive statistics will typically include sample size (N), mean, standard deviation (SD), median, minimum (Min.), and maximum (Max.) as appropriate for continuous variables. For categorical data, the frequency counts and proportions will be computed.

Term	Percentage
GMOs	95
Organic	93
Natural	92
Artificial	65
GMOs	95
Organic	93
Natural	92
Artificial	65
GMOs	95
Organic	93
Natural	92
Artificial	65
GMOs	95
Organic	93
Natural	92
Artificial	65

1 INTRODUCTION

This document summarizes the statistical methods to be implemented during the analysis of data for the evaluation of corneal flap creation using Cheetah femtosecond laser system and Cheetah patient interface. [REDACTED]

The investigators will use the Cheetah femtosecond laser, with the following possible procedures performed: 1) A comparison between the one piece PI (study eye) and two piece PI (control) with the Cheetah system in both eyes and/or 2) A comparison of commercial iFS femtosecond laser (IntraLase iFS) and PI (control) in one eye and the Cheetah femtosecond laser (with the one or two piece PI; study) on the other eye, both to create a LASIK flap on subjects' corneas.

| The eye to receive Cheetah flap will be randomized (ratio of 1:1 for right eye and left eye) and will be considered the study eye. Subjects █ will undergo refractive correction via corneal ablation on both eyes using a commercial excimer laser for vision correction (same excimer laser system will be used on both eyes).

The primary endpoint is the proportion of subjects with a score ≥ 3 in

stromal bed surface quality

Other endpoints include [REDACTED]
[REDACTED]
[REDACTED] anterior segment optical coherence tomography (OCT), [REDACTED]
[REDACTED] adverse events, [REDACTED]
[REDACTED]

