PROTOCOL: A Prospective, Multi-Center Evaluation of Corneal Flap Creation Using Cheetah Femtosecond Laser System and Cheetah Patient Interface.

Protocol Number: CHTA-103-FLAP

STUDY TREATMENTS: Investigational Product:

1) Cheetah system

2) Cheetah Patient Interface (one or two piece)

Control Product:

1) IntraLase FS

2) Cheetah system with [REDACTED] PI

STUDY OBJECTIVE: This is a [REDACTED] prospective clinical trial to clinically optimize the Cheetah femtosecond laser settings for flap creation [REDACTED] and evaluate the flap quality of the Cheetah system [REDACTED]

[REDACTED]
[REDACTED]
[REDACTED]
[REDACTED]
[REDACTED]

OVERALL STUDY DESIGN:

[figure not shown]
Structure: Prospective, randomized (ratio of 1:1 for right eye and left eye, [REDACTED] multicenter, interventional study.

Number of sites: Up to 5 sites

[REDACTED]
[REDACTED]
[REDACTED]
[REDACTED]
[REDACTED]

STUDY POPULATION CHARACTERISTICS:

Number of Subjects: Up to 30 treated subjects in phase I. In Phase II, a minimum of 40 eyes treated with optimized Cheetah settings are needed. Up to 300 subjects may be treated in both eyes (one study eye, and one control) to achieve the minimum 40 eyes with optimized settings and additional eye data for further device experience.

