**DATA ANALYSIS:**

[figure not shown]
the key evaluation stromal bed surface quality, using the investigational vs control product. The analysis population will include both eyes of all treated subjects and will be used for all end points. An interim database lock may be performed after approximately 40 subjects have been treated with optimized settings and reached the 1-month postoperative follow-up.

A large rectangular area of the page has been completely blacked out, indicating redacted content.

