9.5 STUDY PATIENT INTERFACE (PI) SUPPLY

For each subject, one investigational Cheetah PI [REDACTED] and one commercial IntraLase iFS PI (when needed) shall be available. Investigational Cheetah PIs will be obtained from the site investigational PI consignment, supplied by JJSV prior to study initiation and as needed during the study. Commercial IntraLase iFS PIs will be obtained from the site's own inventory. Two PIs [REDACTED] should be available for each case: a primary and a back-up PI. Unused back-up investigational PIs are to be returned to the site consignment. At the completion of study enrollment, any remaining

- Evaluation of flap quality - [REDACTED] bed surface, [REDACTED] through investigator questionnaire

- [REDACTED]
- [REDACTED]
- [REDACTED]
- Adverse event/complications
- [REDACTED]
- [REDACTED]

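### Does the study-eye sentence in SAP section 1 leave the study eye, or the 40-eye minimum, undefined when both eyes receive Cheetah?

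*SAP*

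**What the plan says.** SAP section 1 (Introduction) allows two procedures, joined by and/or:

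- Comparison 1: "A comparison between the one piece PI (study eye) and two piece PI (control) with the Cheetah system in both eyes".
- Comparison 2: the commercial iFS laser and its PI as control in one eye, and "the Cheetah femtosecond laser (with the one or two piece PI; study) on the other eye".

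The next paragraph adds that the "eye to receive Cheetah flap will be randomized (ratio of 1:1 for right eye and left eye) and will be considered the study eye". SAP 2.4 and Protocol 9.4 describe the 1:1 randomization as being between study eye and control eye, without naming a device.

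The primary endpoint (SAP 5.1) is counted per subject. One score from 1 to 5 compares the study eye with the control eye, and the endpoint is the proportion scoring 3 or more. It comes with a two-sided 95% interval by the normal approximation, and the expectation is at least 90%.

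On size, the Protocol synopsis says that in Phase II "a minimum of 40 eyes treated with optimized Cheetah settings are needed", and that up to 300 subjects may be "treated in both eyes (one study eye, and one control) to achieve the minimum 40 eyes with optimized settings". Its Data Analysis paragraph says "An interim database lock may be performed after approximately 40 subjects have been treated with optimized settings". Its product list gives "Cheetah Patient Interface (one or two piece") as investigational. It also lists, among the controls, the Cheetah system with a PI whose description is redacted. Protocol 9.5 says "one commercial IntraLase iFS PI (when needed) shall be available", so the iFS comparison may not apply to every subject.

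**The concern.** Two things look unsettled.

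First, in comparison 1 both eyes receive a Cheetah flap, so a definition based on receiving Cheetah names both eyes or neither. The score has a direction: with the labels reversed, a score s would be recorded as 6 − s. A 4 or 5 in favour of the study eye would become a 2 or 1 and change sides of the cut at 3.

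Second, the minimum is stated in eyes and the endpoint in subjects. In comparison 1 the control eye is also a Cheetah eye. If it counted toward the 40, the minimum could be met with fewer scored pairs, and the primary proportion would be less precise.

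A related query is whether the primary proportion is tabulated by type of control. A score of 3 means similar to a different comparator in each comparison, and the two piece PI is control in comparison 1 but may be the study product in comparison 2.

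**Working it through.** **1. Which eye is the study eye?** The relevant statements, by comparison:

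| Source | Comparison 1 (Cheetah in both eyes) | Comparison 2 (iFS against Cheetah) |
|---|---|---|
| SAP 1, description of procedures | one piece PI eye | Cheetah eye |
| SAP 1, randomization sentence | does not separate the eyes | Cheetah eye |
| SAP 2.4 and Protocol 9.4 | study eye against control eye | study eye against control eye |

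Only one cell fails. The row above it supplies the answer, and nothing in the table names a different eye. Each pair is therefore scored in the intended direction under either comparison.

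**2. Does the count depend on that sentence?** No. If the sentence is reworded to name the one piece PI eye in comparison 1, it is still not stated whether a Cheetah control eye counts toward the 40. The count turns only on what the synopsis means by eyes treated with optimized Cheetah settings.

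**3. How far could the count move?** The plan's 40 cannot be reproduced, because no power, margin, null proportion or sample-size formula is visible. The conversion from eyes to subjects can be shown. Let x be the share of subjects in comparison 1. The documents do not give x, so the full range is used.

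- Only study eyes count: one eye per subject, so 40 eyes = 40 subjects for any x.
- Every Cheetah eye counts, and control eyes also have optimized settings: subjects = 40/(1 + x). For x = 0, 0.25, 0.5, 0.75 and 1 this gives 40, 32, 26.7, 22.9 and 20, or 40, 32, 27, 23 and 20 whole subjects.

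**4. Which reading does the text support?** The synopsis pairs one study eye with one control in the very clause that refers back to the minimum of 40 eyes, which suggests one counted eye per subject. The optional interim lock is set at about 40 subjects on optimized settings, which equals 40 eyes only if one eye per subject is counted. Listing both PI types as investigational describes products and is not a counting rule; the same list has a Cheetah configuration among the controls.

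**5. What would it do to precision?** The SAP's interval is p ± 1.96 × √(p(1 − p)/n). At an observed p = 0.90:

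- n = 40 (36/40): 1.96 × √(0.09/40) = 0.093, so 80.7% to 99.3%.
- n = 20 (18/20): 1.96 × √(0.09/20) = 0.1315, so 76.9% to 103.1%.
- The upper limit stays within 100% when n ≥ 1.96² × 0.09/0.10² = 34.6, that is from n = 35.

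The cutoff of 35 holds only at exactly 90%. At 32/35 (91.4%) the upper limit is 0.914 + 0.093 = 1.007, and at 37/40 (92.5%) it is 0.925 + 0.082 = 1.007. The overshoot belongs to the normal approximation near 100%; neither the study-eye sentence nor the counting unit causes it. For comparison, Wilson intervals are 76.9% to 96.0% for 36/40 and 69.9% to 97.2% for 18/20.

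**The case for a change.** The strongest case for a change is that the conflict lies in visible text and needs no guess about redactions. A directional score deserves one definition of the study eye, no visible line says whether a Cheetah control eye counts toward the 40, and rewording would cost two short edits and no data.

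Part of this stands. The SAP 1 sentence fits only comparison 2 if taken literally, and the synopsis does not state its minimum in the unit of the endpoint. The rest does not carry through. The definition that is needed is given one paragraph earlier. The figure of 20 is a literal lower bound that requires three unstated conditions together: all subjects in comparison 1, all control eyes on optimized settings, and all of them counted. If study eyes are meant, as the text suggests, the edits would leave every subject number as it is.

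The query about a table by control type is sensible in itself, but it arises only if both comparisons are run. The text around the analysis population and primary analysis (Protocol 19.1 and 19.2, SAP 2.1 and 5.1) is heavily redacted, so such a table cannot be called absent. Advice to use a different interval for small groups depends on the same hypotheticals.

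**Conclusion.** No change to the plan follows. The study-eye sentence is a clerical slip that the same SAP section resolves: in comparison 1 the study eye is the one piece PI eye. The eyes-or-subjects wording is a gap that an analyst fills by counting study eyes, which gives about 40 scored subjects.

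If the most extreme alternative reading were meant, the minimum would be 20 scored subjects, and the half-width at an observed 90% would rise from 9.3 to 13.1 points. No visible power calculation, precision target or decision rule depends on that difference, and up to 300 subjects are allowed.

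This rests on two assumptions: that the one piece PI label in SAP 1 governs comparison 1, and that the redacted text does not define the 40 differently. On the visible text, rewording either sentence would not alter any result the plan would produce.

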2 ANALYSIS POPULATIONS

2.1 ANALYSIS POPULATIONS

The analysis population [REDACTED] will be both eyes [REDACTED] treated subjects and will be used for all endpoints [REDACTED]

Term	Percentage
Climate change	92
Global warming	100
Green energy	95
Carbon footprint	88
Sustainable development	93
Renewable energy	90
Emissions reduction	85
Green economy	94
Carbon tax	87
Carbon pricing	91

2.3 DATA CONVENTIONS

Descriptive statistics will typically include sample size (N), mean, standard deviation (SD), median, minimum (Min.), and maximum (Max.) as appropriate for continuous variables. For categorical data, the frequency counts and proportions will be computed.

[REDACTED]

[REDACTED]

[REDACTED]

[REDACTED]

2.4 RANDOMIZATION

A randomization list stratified by site will be created [REDACTED]
[REDACTED] Subjects' eyes [REDACTED] will be
randomized on a 1:1 basis between the study eye and the control eye.

3 ACCOUNTABILITY/DEMOGRAPHICS

Demographics/enrollment/accountability data and binocular data will be reported for all subjects.

3.1 ACCOUNTABILITY

The number of enrolled subjects will be tabulated by site. Subject accountability will be summarized as a frequency distribution by scheduled visits. The frequency counts and proportions of available subjects, including those outside of the interval, and the frequency and proportion of missing subjects (forms not yet completed, active, missed visit, lost to follow-up or discontinued) will be reported.

3.2 DEMOGRAPHICS

Subject demographic data including age, sex, race and ethnicity will be presented. Age will be summarized with descriptive statistics with mean, standard deviation, minimum and maximum. The frequency distributions of sex, race and ethnicity will be tabulated.

3.3 PREOPERATIVE PARAMETERS

© 2019 Pearson Education, Inc.

www.english-test.net

11. **What is the primary purpose of the *Journal of Clinical Endocrinology and Metabolism*?**

10. *Journal of the American Statistical Association*, 1990, 85, 200-207.

1. **What is the primary purpose of the study?** (e.g., to evaluate the effectiveness of a new treatment, to explore a new research question, to describe a population, etc.)

[REDACTED]

Black bars redacted for security reasons.

5 STUDY ENDPOINTS

5.1 PRIMARY STUDY ENDPOINTS

██████████ stromal bed surface quality, ██████████ of the study eye will be evaluated relative to the control eye on a scale of 1 to 5, with higher scores indicating a better performance of the study eye over the control eye. The scoring is as follows:

- 1 – Control eye is much better than study eye
- 2 – Control eye is better than study eye
- 3 – Study eye is similar to control eye
- 4 – Study eye is better than control eye
- 5 – Study eye is much better than control eye

The frequency counts and proportions of the final score will be reported ██████████
█████ stromal bed surface quality ██████████.

The primary endpoint is the proportion of subjects with a score ≥ 3 in ██████████
██████████ surface quality ██████████.

Analysis of The Primary Endpoint

The counts and proportions of subjects with a score ≥ 3 in ██████████
█████ surface quality ██████████ will be tabulated. The 95% two-sided CI ██████████ be calculated using the normal approximation method.

At least 90% of subjects are expected to have a score equal to or greater than 3 ██████████
██████████

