5.1 PRIMARY STUDY ENDPOINTS

[REDACTED] stromal bed surface quality, [REDACTED] of the study eye will be graded on a scale of 1-5 relative to the control eye. A score of 3 means that the study eye is similar to the control eye; a score of 4 or 5 means that the study eye is superior to the control eye; and a score of 1 or 2 means that the control eye is superior to the study eye. 90% of all subjects are expected to have a score equal to or greater than 3 [REDACTED].

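### The normal-approximation interval for the primary proportion is unreliable where the plan expects the result: 90% or more, with as few as about 40 subjects

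*SAP*

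**What the plan says.** SAP 5.1 defines the endpoint: "The primary endpoint is the proportion of subjects with a score ≥ 3 in" stromal bed surface quality. Each subject contributes one score, comparing the study eye with the control eye. Under the analysis of the primary endpoint, the SAP adds that "The 95% two-sided CI" will "be calculated using the normal approximation method"; a short redaction sits inside that sentence. It then states: "At least 90% of subjects are expected to have a score equal to or greater than 3". Protocol 5.1 has the same expectation: "90% of all subjects are expected to have a score equal to or greater than 3".

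On size, the protocol synopsis (Number of Subjects) says that in Phase II "a minimum of 40 eyes treated with optimized Cheetah settings are needed", and that "Up to 300 subjects may be treated in both eyes". The synopsis Data Analysis paragraph adds: "An interim database lock may be performed after approximately 40 subjects have been treated with optimized settings". The visible text gives no formula for the interval, no other method for proportions near 100%, and no comparison of either limit with 90%.

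**The concern.** The usual normal-approximation interval takes its width from the observed proportion. Near 100% the estimated standard error shrinks towards zero while the sampling distribution is skewed, so the interval is too short and sits too high. By the plan's own figures the trial is in that region: 40 × (1 − 0.90) = 4 expected failures at the minimum size, and fewer if the device does better than 90%.

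This is the only interval visible for the primary endpoint. If it is too short on the low side, the report overstates how firmly the data exclude poorer performance. A perfect result in 40 subjects would come out as 100% (100% to 100%), which claims certainty from 40 observations.

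**Working it through.** The documents give no numerical interval, power or sample-size calculation, so there is no stated figure to reproduce. The check applies the SAP's method and computes its true coverage.

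**Inputs**
- 95% two-sided, so z = 1.960 (SAP 5.1).
- n = 40 (protocol minimum and possible interim lock) up to 300 (protocol maximum). With one study eye and one score per subject, 40 study eyes are 40 subjects. The final n is not visible, so a range is shown.
- True proportion p from 0.90 to 0.99. This is an assumption, because the documents say only 90% or at least 90%.
- Normal approximation is read as Wald: p̂ ± 1.960 × √(p̂(1 − p̂)/n). This is also an assumption.

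**Step 1: intervals at n=40.** For 39/40, p̂ = 0.975 and √(0.975 × 0.025/40) = 0.0247. The limits are 0.975 ± 1.960 × 0.0247, or 92.7% to 102.3%.

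| Result | Wald | Wilson | Clopper-Pearson |
|---|---|---|---|
| 36/40 | 80.7 to 99.3% | 77.0 to 96.0% | 76.3 to 97.2% |
| 37/40 | 84.3 to 100.7% | 80.1 to 97.4% | 79.6 to 98.4% |
| 38/40 | 88.3 to 101.8% | 83.5 to 98.6% | 83.1 to 99.4% |
| 39/40 | 92.7 to 102.3% | 87.1 to 99.6% | 86.8 to 99.9% |
| 40/40 | 100 to 100% | 91.2 to 100% | 91.2 to 100% |

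**Step 2: exact coverage at n=40.** Coverage is the sum of Binomial(n, p) probabilities over every count whose interval contains p. At p = 0.90 the Wald interval contains 0.90 for counts 31 to 38. It misses high for 39 or 40 (6.57% + 1.48% = 8.05%) and low for 30 or fewer (0.51%). Coverage is 100 − 8.05 − 0.51 = 91.4%. A 95% interval should miss 2.5% on each side.

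| True p | Wald | Wilson | Clopper-Pearson |
|---|---|---|---|
| 0.90 | 91.4% | 94.3% | 97.0% |
| 0.925 | 80.4% | 97.2% | 99.1% |
| 0.95 | 86.8% | 95.2% | 98.6% |
| 0.97 | 70.3% | 96.9% | 99.3% |
| 0.98 | 55.3% | 95.4% | 99.2% |

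The figures jump about because counts are discrete. On a grid of 901 values of p from 0.90 to 0.99, Wald reaches 95% at none. Its mean coverage there is 79.0%, against 95.6% for Wilson and 98.4% for Clopper-Pearson.

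**Step 3: chance of an impossible or zero-width interval at n=40.** This is P(X ≥ 37): 42.3% at p = 0.90, 64.7% at 0.925 and 86.2% at 0.95. The zero-width case alone (40/40) has probability 1.5%, 4.4% and 12.9%.

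**Step 4: larger n.** Wald coverage at p = 0.90 is 93.2% (n=100), 92.6% (n=150) and 93.8% (n=300). The means over 0.90 to 0.99 are 89.4%, 91.5% and 93.1%.

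**Step 5: would a continuity correction help?** Not at n=40: mean coverage is 82.8%, and 40/40 gives 98.8% to 101.2%.

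**Step 6: only if the lower limit were compared with 90%.** At true p = 0.90, Wald would clear 90% with probability 8.0% (n=40) or 4.6% (n=300). Wilson or Clopper-Pearson would clear it with probability 1.5% or 1.7%. The methods would disagree only at 39/40, or at 279 and 280 of 300.

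**The case against.** The arithmetic is not in dispute; the case against is about weight.

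- **No visible decision uses the interval.** The 90% is worded as an expectation. This stands, and it limits the finding to reported precision. Step 6 matters only if hidden text makes the comparison.
- **Redactions could hide a fallback.** Text is blacked out in and after the interval sentence and in SAP 2.3. A rule for 100% results may exist, so its absence cannot be asserted. The visible method is nevertheless stated without qualification.
- **Wald is an inference.** True. If a score interval was meant, the SAP should name it.
- **Forty is a floor, and the interim lock is optional.** Also true. Nothing visible says the primary interval will be computed at that lock, and more subjects could be in the analysis set. At n=100 to 300 and p = 0.90 the shortfall is about 1 to 2.5 points.
- **The 79.0% mean weights all p up to 0.99 equally.** It is a summary only; the coverage at 0.90, 0.925 and 0.95 makes the point without it.
- **Limits above 100% can be truncated.** They can, but truncation leaves coverage unchanged and does not help at 40/40.
- **A continuity correction works better at larger n.** At n=300 mean coverage is 94.8%. That does not help a lock at about 40.

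**Conclusion.** The concern holds. On the plan's own expectation and minimum size, the prescribed interval does not deliver 95% confidence, and its error favours the device. At n=40 coverage is between 80.4% and 91.4% at the three values 0.90, 0.925 and 0.95, and lower still at 0.97 and 0.98. At n=300 the loss is modest for p = 0.90 to 0.98 (92.6% to 93.8% at the values computed) but large at 0.99 (79.9%).

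The conclusion rests on reading normal approximation as Wald, on a true proportion of 0.90 or above, and on n near 40 for the larger figures. It should be fixed, but it is not fatal: no visible success rule depends on it, and the point estimate does not change.

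**What to change.** In SAP 5.1, replace the normal approximation with the Wilson score method, or with the exact Clopper-Pearson method if coverage must never fall below 95%. Apply the same method at any interim lock and at the final one. The change is right whether 90% is meant for the estimate or for the lower limit.

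The cost is one phrase in the SAP and one option in the analysis code; design, sample size and endpoint are untouched. The lower limit becomes less favourable: by 3.8 (Wilson) to 4.4 (Clopper-Pearson) points at 36/40, 5.5 to 5.8 at 39/40, 8.8 at 40/40, and about 0.5 at 270/300. Neither method is perfect at n=40. Wilson falls to 89.5% coverage at its worst p between 0.90 and 0.99. Clopper-Pearson stays at 95.3% or above but is wider than it needs to be.
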